Brain Imaging	X (See note)	X (See note)	Primary CNS neoplasms: MRI without and with contrast should have MRI of the brain approximately every 12 weeks (± 7 days) until BICR confirmation of disease progression or treatment discontinuation (including treatment beyond progression), whichever comes later. For Solid Tumors: Participants with a history of brain metastasis or symptoms should have a surveillance brain MRI per standard of care (approximately 12 weeks) or sooner if clinically indicated. See Section 9.1 for further details.
Other: Bone Scan	X (See note)	X (See note)	As clinically indicated per local standards. See Section 9.1 for further details.
Participant status		X	Every 3 months after X02; may be accomplished by visit or phone contact, to update survival information Collect all subsequent anti-cancer treatment.

^a Participants must be followed for at least 100 days after last dose of study treatment. Follow-up visit #1 (FU1) occurs approximately 30 days (± 7 days) after the last dose or coinciding with the date of discontinuation (± 7 days) if date of discontinuation is greater than 30 days after last dose. Follow-up visit #2 (FU2) occurs approximately 100 days (± 7 days) from last dose. Both FU1 and FU2 should be conducted in person.

- ^b Survival Follow-up visits to occur every 3 months \pm 14 days from Follow-up Visit 2. BMS may request that survival data be collected on all treated participants outside of the protocol window. At the time of this request, each participant will be contacted to determine their survival status unless the participant has withdrawn consent for all contacts. Survival follow-up may be conducted in person or by telephone.

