8.1.3 Post Study Treatment Study Follow-up

In this study, overall survival is a key endpoint of the study. Post treatment follow-up is of critical importance and is essential to preserving participant safety and the integrity of the study. Participants who discontinue study treatment must continue to be followed for collection of outcome and/or survival follow-up data as required and in line with [Section 5](#) until death or the conclusion of the study.

BMS may request that survival data be collected on all treated/randomized participants outside of the protocol defined window (See [Table 2-5](#) in Schedule of Activities). At the time of this request, each participant will be contacted to determine their survival status unless the participant has withdrawn consent for all contacts or is lost to follow-up.

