9.2.1 Time Period and Frequency for Collecting AE and SAE Information

The collection of non-serious AE information (with the exception of non-serious AEs related to SARS-CoV-2 infection) should begin at initiation of study treatment and for a minimum of 100 days following discontinuation of study treatment and at the timepoints specified in the Schedule of Activities ([Section 2](#)).

Sections 5.6.1 and 5.6.2 in the Investigator Brochure (IB) represent the Reference Safety Information to determine expectedness of serious adverse events for expedited reporting.

Following the participant's written consent to participate in the study, all SAEs, whether related or not related to study drug, must be collected, including those thought to be associated with protocol-specified procedures.

All SAEs and all AEs (SAEs and non-serious AEs) associated with confirmed or suspected SARS-CoV-2 infection must be collected from the time of signing the consent, including those thought to be associated with protocol-specified procedures and until 100 days following discontinuation of dosing.

Note: for participants who signed a pre-screening consent with submission of an archived tumor sample for eligibility assessment, SAE collection will start at the time of signature of the full informed consent. For participants who signed a pre-screening consent to agree to collection of a fresh biopsy, SAE collection will start at the time of signature of the pre-screening informed consent.

For participants randomized and never treated with study drug, SAEs should be collected for 30 days from the date of randomization.

The investigator must report any SAE that occurs after these time periods and that is believed to be related to study drug or protocol-specified procedure, (eg, a follow-up skin biopsy).

- Medical occurrences that begin before the start of study treatment but after obtaining informed consent will be recorded on the appropriate section of the eCRF module.
- All SAEs will be recorded and reported to Sponsor or designee within 24 hours, as indicated in [Appendix 3](#).
- The investigator will submit any updated SAE data to the sponsor or designee within 24 hours of updated information being available.

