
The investigator-assessed ORR
	
Investigator-assessed ORR will be summarized by binomial response rates and their corresponding two-sided 95% exact CIs using Clopper-Pearson method.

The investigator-assessed DOR
	
Investigator- assessed duration of response (DOR) will be estimated for all randomized participants who achieve confirmed PR or CR using the Kaplan-Meier (KM) product-limit method. Median values of DOR, along with two-sided 95% CI using Brookmeyer and Crowley method, will also be calculated. Probability of achieving $DOR \geq 6$ months will be calculated using KM method with 95% CI.

TTR is defined as the time from randomization date to the date of the first confirmed response, as assessed by the BICR.
	
Time to response (TTR) will be summarized using descriptive summary statistics for the responders.

Endpoint Definition	Statistical Analysis Methods

CBR is defined as the number of participants with a best overall response (BOR) of confirmed complete response (CR) or partial response (PR) or stable disease (SD) divided by the number of randomized participants.
	
BICR and Investigator assessed CBR will be summarized by binomial response rates and their corresponding two-sided 95% exact CIs using Clopper-Pearson method.

OS is defined as the time from the randomization date to the date of death.
	
Time to event distribution will be estimated using Kaplan Meier techniques. Median OS along with 95% CI will be constructed based on a log-log transformed CI for the survivor function. Rates at some fixed timepoints (6, 12, 18 and 24 months) will be derived from the Kaplan Meier estimate and corresponding confidence interval will be derived based on Greenwood formula for variance derivation and on log-log transformation applied on the survivor function.
 
Participants without documentation of death will be censored on the last date the participant was known to be alive.

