
PFS is defined as the time from randomization date to the date of the first documented tumor progression, determined by BICR assessments (per RECIST 1.1 or RANO), or death due to any cause, whichever occurs first.
	
BICR and investigator assessments will use Response Evaluation Criteria in Solid Tumors (RECIST 1.1), and Response Assessment for Neuro-Oncology (RANO) criteria for primary CNS neoplasms.
 
Participants without a reported progression will be considered to have progressed on the date of their death if no subsequent anti-cancer therapy initiated.
 
Participants who did not progress or die will be censored on the date of the last tumor assessment.
 
Participants who did not have any on study tumor assessments and did not die will be censored on the first dosing date. Participants who started any subsequent anti-cancer therapy and without a prior reported progression will be censored at the last tumor assessment prior to initiation of the subsequent therapy.
 
Time to event distribution will be estimated using Kaplan Meier techniques. Median PFS along with 95% CI will be constructed based on a log-log transformed CI for the survivor function. Rates at some fixed time points (6, 12, 18 and 24 months) will be derived from the Kaplan Meier estimate and corresponding confidence interval will be derived based on Greenwood formula for variance derivation and on log-log transformation applied on the survivor function.

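### Randomized but never-treated participants have no scheduled survival contact, Table 2-5 and Section 8.1.3 disagree on whether survival requests reach them, and their PFS censoring date is undefined

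*Combined protocol and SAP*

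**What the plan says.** Section 10.3 sets the default analysis population as all randomized participants in the salvage setting, grouped as randomized. Section 10.3.1 gives the OS time origin: "OS is defined as the time from the randomization date to the date of death". PFS has the same origin. OS without a documented death is censored at the last date the participant was known to be alive.

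Table 2-5 builds follow-up on dosing. Footnote a says "Participants must be followed for at least 100 days after last dose of study treatment" and places Follow-up Visit 2 at about 100 days from that dose. The participant-status row then reads "Every 3 months after X02; may be accomplished by visit or phone contact, to update survival information". Scheduled body imaging is counted from the first dose.

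Two places describe the sponsor's right to ask for survival data between scheduled contacts:
- Table 2-5, footnote b: "BMS may request that survival data be collected on all treated participants outside of the protocol window".
- Section 8.1.3, which cites Table 2-5: "BMS may request that survival data be collected on all treated/randomized participants outside of the protocol defined window".

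The protocol foresees participants who never start treatment. Section 9.2.1 has the explicit rule: "For participants randomized and never treated with study drug, SAEs should be collected for 30 days from the date of randomization". Section 9.2.4 repeats it. Neither mentions survival.

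For PFS, Section 10.3.1 adds: "Participants who did not have any on study tumor assessments and did not die will be censored on the first dosing date".

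**The concern.** The follow-up schedule and the analysis population do not match. The analysis counts everyone from randomization, whereas the schedule starts from a dose that some randomized participants may never receive. For them the scheduled visits have no anchor, and the fallback request includes or excludes them depending on which page the site reads.

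In a salvage population, failure to start treatment is plausibly linked to early deterioration. If contact with those participants stops early, later deaths may go unrecorded and the censoring may be informative. An OS curve labelled all randomized would then drift towards OS in the treated. Section 8.1.3 itself calls OS a key endpoint and stresses post-treatment follow-up, so the gap runs against the protocol's stated aim.

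The PFS rule is a separate drafting fault. It asks for a date that does not exist for the never-treated. Even for treated participants it is not the date from which PFS is counted.

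**Working it through.** **1. Which provisions reach a participant who was randomized but never dosed**

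| Provision | Anchor or population | Reaches the never-treated? |
|---|---|---|
| Follow-up Visits 1 and 2 (Table 2-5) | last dose; Visit 1 may shift to the discontinuation date, Visit 2 may not | no |
| Survival visits (Table 2-5) | Follow-up Visit 2, hence last dose | no |
| Body imaging (Table 2-5) | first dose | no |
| Ad hoc survival request, footnote b | treated | no |
| Ad hoc survival request, Section 8.1.3 | treated/randomized | yes, if the sponsor asks |
| Follow-up duty, Section 8.1.3 | those who discontinue treatment | unclear |
| SAE collection, Sections 9.2.1 and 9.2.4 | 30 days from randomization | yes |
| Vital-status efforts, Sections 8.2 and 8.3 | public sources under local law; tracing of those lost to follow-up | possibly |

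The last contact that is both scheduled and explicit is therefore the end of the 30-day SAE window. Death is an SAE outcome (Appendix 3), so deaths inside that window are captured. Later deaths depend on provisions that are discretionary, conditional or unclear.

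**2. Possible size for OS**

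The plan states no figure for this group, so there is nothing to reproduce. The planned total used for scaling does reproduce from Section 10.1: 1.5 × (76 + 76 − 76 × 0.40) = 182.4, stated as 183.

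Let f be the never-treated share, S_t the 12-month OS in the treated and S_u that in the never-treated. None of these is in the documents. The assumptions are f = 1%, 3% or 5%, S_t = 55%, and S_u = 10%, 30% or 55%.

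- OS in all randomized = (1 − f) × S_t + f × S_u.
- In the extreme case where every never-treated participant is censored at day 0, Kaplan-Meier estimates S_t.
- Overstatement = f × (S_t − S_u). For example, 0.05 × (0.55 − 0.10) = 0.0225.

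| f | of 183 | of 76 | S_u = 55% | S_u = 30% | S_u = 10% |
|---|---|---|---|---|---|
| 1% | 1.8 | 0.8 | 0 | 0.25 points | 0.45 points |
| 3% | 5.5 | 2.3 | 0 | 0.75 points | 1.35 points |
| 5% | 9.2 | 3.8 | 0 | 1.25 points | 2.25 points |

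Sampling error for comparison: √(0.55 × 0.45 / 76) = 0.057, or 5.7 points.

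The day-0 case is a bound. If deaths to day 30 are known and the remaining never-treated are censored then, the overstatement is f × (S_u30 × S_t / S_t30 − S_u), where S_t30 and S_u30 are 30-day survival in the treated and never-treated. When S_u30 is no higher than S_t30, this cannot exceed f × (S_t − S_u). Deaths or vital status learned later reduce it further.

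**3. PFS**

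The rule applies to participants with no on-study assessment and no death. A treated participant should start within 3 calendar days of randomization (Sections 7.1.1 and 7.1.2), so the rule gives that person up to about 3 days of PFS time. A never-treated participant has no dosing date, so the rule returns nothing. Moving the censoring date to randomization shifts a treated case by those few days at most and defines the untreated case. The effect on the curve is essentially nil.

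**4. ORR**

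The denominator in Section 10.3.1 is all randomized participants, so a never-treated participant counts as a non-responder and the primary endpoint is untouched.

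**The case against.** Much of the opposing case stands, and it limits the point.

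- A reader might infer from footnote b that survival requests are confined to treated participants throughout the protocol. They are not: Section 8.1.3 governs the same request, includes randomized participants and says each will be contacted for survival status. The defect is a conflict between two passages.
- A reader might also infer that these participants' OS is censored almost at entry. No rule says so. Censoring is at the last date known alive, any documented death counts, early deaths are collected as SAEs, and Sections 8.2 and 8.3 allow vital status to be sought elsewhere. Early censoring is a risk if Table 2-5 is followed alone.
- Arm-specific refusal in an open-label trial might suggest a distorted comparison between arms. The documents do not support that: Section 10.1 calls the monotherapy arm non-comparative, Section 10.3.1 plans no OS or PFS comparison, and nothing shows that failure to start differs by arm.
- The numbers are assumed, and the short interval between randomization and dosing suggests few cases. Even the bound is below half the standard error.
- Section 10.3 leaves missing-data procedures to a statistical analysis plan, where the PFS date could be settled.

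What the objection does not supply is a scheduled contact. The ad hoc request is optional, public searches depend on local law, and the continuing duty is worded for people who stopped treatment, not for people who never began. A later analysis plan can define a censoring date, but it cannot recover contacts that were never made.

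**Conclusion.** The point holds as a minor one. Three things are established from the text: footnote b and Section 8.1.3 name different populations for the same survival request; a group that the protocol foresees has no scheduled survival contact beyond 30-day SAE collection, although OS and PFS include it from randomization; and the PFS no-assessment rule gives that group no usable date and does not match the randomization origin.

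The consequence is a risk of small bias in descriptive secondary estimates. The upward direction is probable, not proven: it requires the never-treated to survive worse than the treated, and it would reverse if they survived better. The 0 to 2.25 points are an illustrative bound that depends wholly on the assumed rate and survival values.

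**What to change.** Three wording changes:

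1. Table 2-5, footnote b: change the population from treated to all randomized participants, in line with Sections 8.1.3 and 10.3.
2. Table 2-5: add that participants randomized but never treated have survival contact every 3 months from the randomization date, with telephone allowed as it already is for survival follow-up.
3. Section 10.3.1: censor PFS at the randomization date for participants with no on-study tumor assessment and no death. This corrects a date and has essentially no numerical effect.

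The cost is three sentences and telephone calls to what is probably a handful of participants. OS may come out slightly lower. The request for extra survival data can stay at the sponsor's discretion; nothing here requires a compulsory sweep before each data cut-off.

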3 INTRODUCTION

Blockade of the PD-1 pathway has proven effective in generating robust anti-tumor immune responses. Nivolumab, an anti-PD-1 blocking antibody, has demonstrated overall survival benefit in multiple tumors including non-squamous cell lung cancer, squamous cell lung cancer, melanoma, renal cell carcinoma and head and neck cancer. Recent data across multiple tumor types support the hypothesis that patients with tumors harboring increased somatic mutations due to DNA mismatch-repair deficiencies are more likely to respond to anti-PD-1/PD-L1 and anti-CTLA-4 blockade. Tumor mutational burden (TMB) refers to the total number of somatic mutations that exist within a tumor's genome. A subset of these mutations may result in expressed proteins that are not recognized by the host's immune system as self, and therefore has the potential to be immunogenic and more susceptible to immune-mediated anti-tumor response. The primary goal of this study is to demonstrate the clinical activity of nivolumab in combination with ipilimumab in multiple tumor types based on the status of TMB.

3.1 Study Rationale

3.1.1 *Rationale for Participant Population with TMB-H Tumor*

[figure not shown]
Tumors with a high mutational burden may have a higher number of neo-antigens which, in principle, would be expected to be more immunogenic than tumors with comparatively low mutational burden.¹ Therefore, high TMB has been hypothesized to correlate with improved efficacy in patients treated with immune-oncology (IO) therapies. This hypothesis has been supported by multiple publications across IO therapies, tumor types, and lines of treatment. The first published study of TMB as a biomarker of clinical outcomes was reported by Snyder et al, where high TMB (TMB-H) was found to be associated with efficacy in metastatic melanoma patients treated with anti-CTLA-4 therapy. Further studies by Rizvi et al reported TMB as a biomarker of pembrolizumab efficacy in second-line NSCLC patients.¹ Additional studies of pembrolizumab and atezolizumab in NSCLC have been generally consistent with these results.²

Furthermore, TMB was evaluated in an exploratory post hoc analysis in the BMS-sponsored first line NSCLC study, CheckMate 026, which represents the first phase 3 study to demonstrate the impact of TMB on efficacy of a PD-1/L1 inhibitor.³ This analysis demonstrated that in patients with TMB-H, the ORR was numerically higher in the nivolumab arm versus the chemotherapy arm (47% vs 28%) and the median PFS was longer in the nivolumab arm compared to the chemotherapy arm (9.7 vs 5.8 mo., HR 0.62; 95% CI 0.38, 1.00). OS was notable, though similar (18.3 vs 18.8 mo. and 1 year OS rates of 64% vs 60%, respectively), between the arms in patients with TMB-H, although of note, 68% of patients in the chemotherapy arm received subsequent nivolumab.⁴ Interestingly, the ORR and mPFS rates observed in the TMB-H subgroup in the nivolumab arm within CheckMate 026 were similar to those reported in the first line NSCLC study of pembrolizumab (Keynote-024), where ORR and mPFS were 45% and 10.3 months, respectively, in patients with $\geq 50\%$ PD-L1 expression treated with pembrolizumab monotherapy.⁵ Results from CA209227 showed that nivolumab combined with ipilimumab, as first line treatment in patients with metastatic NSCLC of TMB ≥ 10 mut/Mb, demonstrated significantly better and durable clinical response and progression-free survival benefit compared to chemotherapy,

including ORR 45.3% vs 26.9%, DOR ≥ 1 yr 68% vs 25%, PFS rate at 1 yr 43% vs 13%, and mPFS of 7.2 vs 5.4 months. Preliminary analysis on OS was also encouraging, and the clinical benefits are independent of PD-L1 expression. These findings further support TMB as an important, predictive and independent biomarker for clinical efficacy.

Recently, Yarchoan M, et al suggested a significant positive linear correlation between higher TMB and increased ORR after analyzing 27 tumor types/subtypes treated with anti-PD-1/PD-L1 monotherapy, which highlights the potential strong relationship between TMB and the clinical activity of anti-PD-1/PD-L1 therapies across multiple cancers.⁶

[figure not shown]
Figure 3.1.1-1: Correlation between Tumor Mutational Burden and Objective Response Rate with Anti-PD-1 or Anti-PD-L1 Therapy

Taken together, the available data suggest that, in addition to PD-L1, TMB is also an important predictive biomarker of the clinical efficacy of IO therapy. Therefore, patients of TMB-H across multiple solid tumors will be selected for participation in this clinical study.

Prevalence of TMB-H tumor: Selected tumors and their corresponding prevalence by TMB are shown in the figure below:

Figure 3.1.1-2: Tumor Mutational Burden in Various Tumor Types

Analyzed using an algorithm developed to extract mutational signatures from catalogues of somatic mutations in 7042 primary cancers. Source: adapted from Alexandrov LB, et al. Nature 2013;500:415-21⁷

3.1.2 Rationale for Study in Refractory, Metastatic, or Unresectable Setting

This trial with nivolumab in combination with ipilimumab and nivolumab monotherapy will include participants with refractory, metastatic or unresectable TMB-H malignancy who have been treated with prior non-IO therapies. In general, malignancies included in this trial are the ones that have no standard of care after first line therapy showing an improved benefit over best supportive care. The low prevalence of TMB-H in these tumor types limits the feasibility of traditional large-scale randomized trials. As a result, a high unmet medical need exists for these patients, with no less expectation for immunotherapy activity.

3.1.3 Rationale for Inclusion of Adolescent Participants

The majority of pediatric patients with cancer are enrolled in clinical trials; however, enrollment has been shown to decrease with age, and only 10% to 15% of older adolescents (ages 12 to 19) with cancer participate in clinical trials and is considered an unmet need. Much of the more than 50% decrease in overall childhood cancer mortality since 1975 has been attributed to clinical trial participation, but survival improvements for adolescents and young adults have historically lagged behind the pediatric population as a whole, and decreased participation in clinical trials may contribute to this finding.

Lack of participation in the pediatric trials may be due to differences in tumors observed in the two groups, as tumors in adolescents may mirror those observed more often in adults. For trials in adult participants with tumor types that also occur in adolescents, adolescents are often excluded due to safety or regulatory concerns. Overall, this has led to a delay in the study of new therapies in adolescents, and most problematically, a delay in new efficacious therapies reaching this population. It has been recommended that adolescents be considered for trials in adult populations

for tumor types that are observed in adolescents and that share features common to those tumors that occur in adults.^{8,9} Thus, adolescents will be included in this study where locally permitted. Individual countries and sites have the option of opting out of adolescent eligibility.

This section is not applicable for sites in Belgium or the Netherlands as adolescents will not be included in these countries.

